The epidural anesthesia will be started at the discretion of the attending anesthesiologist either before or on-arrival to the post-anesthesia care unit. Any additional medications administered during the immediate post-operative period in the post-anesthesia care unit will be prescribed by the attending anesthesiologist and will not be standardized. Beginning when the patient leaves the post-anesthesia care unit, all patients will be given the following pain regimen: acetaminophen (15mg/kg PO or per g-tube every 6 hours around the clock), ketorolac (0.5mg/kg IV every 8 hours for 3 doses) followed by ibuprofen (10mg/kg PO or per g-tube every 8 hours as needed for mild pain (pain score 1-3)), diazepam (0.1mg/kg PO or per g-tube every 6 hours around the clock for 36 hours followed by every 6 hours as needed for muscle spasms), and oxycodone (0.1mg/kg PO or per g-tube every 6 hours as needed for severe pain (pain score 7-10)). Nurses will be instructed to offer this as-needed medication to patients at standardized intervals every 4 hours when performing pain assessments. Additional medication for pain may be administered if the protocol does not result in adequate pain relief, at the discretion of the treating physician. The epidural will be titrated by the acute pain anesthesiology team for inadequate pain control, and all epidurals will be discontinued the morning of post-operative day two. All patients will be discharged on a standardized medication regimen as follows: diazepam (0.1mg/kg PO or per g-tube every 6 hours for 14 days), oxycodone (0.1mg/kg PO or per g-tube every 6 hours as needed for severe pain, 20 doses), acetaminophen (15mg/kg PO or per g-tube every 6 hours for 14 days), and ibuprofen (10mg/kg PO or per g-tube every 8 hours for 14 days). Inpatient and outpatient narcotic consumption will be recorded as morphine equivalents.

All other aspects of post-operative care, including (but not limited to) physical therapy, weight bearing status, mobilization, and bracing will be decided on a case-by-case basis by the treating surgeon.

Data Collection and Protection:

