Data will be collected by IRB-approved research personnel via access to the medical record. Personal identifying information collected will include name, date of birth, medical record number, and telephone number. All data will be labeled with a code that can be linked to this personal identifying information. Data will be collected only from the hospitalization following the surgical procedure and from the first post-operative visit. This data will include: narcotic consumption, pain scores, complications or adverse events, and re-admission in the immediate post-operative period (first two weeks post-operatively). All data will be stored on a secure, encrypted data storage device or password protected and encrypted internet-based storage device.

Outcome Measures:

The primary outcome measure will be total narcotic consumption in the first 48 hours after surgery. Narcotic consumption will be recorded in the medical record while in the post-anesthesia care unit and while inpatient and will be converted into morphine equivalents according to a conversion table. The secondary outcome will be pain scores during inpatient hospitalization following the surgical procedure. Pain score assessments will be completed in the post-anesthesia care unit, and every 4 hours following the surgical procedure. Scores will be collected by nursing staff on the inpatient ward who are blinded to treatment allocation and recorded in the electronic medical record. The type of pain score collection will vary based on patient age and level of intellectual disability. In verbal children, either the VAS or FACES pain scale will be employed. In non-verbal children, the FLACC scale will be employed.

Additional secondary outcome measures will include total narcotic consumption following hospital discharge, length of stay, parent satisfaction scores, and complications. Patients will be instructed to bring their medications with them to their first post-operative visit, and outpatient narcotic use will be recorded based on amount of medication remaining. This will also be converted into morphine equivalents according to the same conversion table. Parent satisfaction scores will be based on a standardized questionnaire taken by parents in person at the first post-operative clinic visit aimed to assess their satisfaction with their child's pain management perioperatively.

Statistical Analysis Plan

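### Post-discharge opioid use is counted from discharge, itself tied to a trial outcome, to an undated visit, so a shorter stay in one arm could be misread as greater opioid need

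*Combined protocol and SAP*

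**What the plan says.** The Outcome Measures section lists the further secondary outcomes in one sentence: "Additional secondary outcome measures will include total narcotic consumption following hospital discharge, length of stay, parent satisfaction scores, and complications". Post-discharge use and length of stay therefore stand side by side. No discharge criteria or fixed discharge day are given.

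The post-discharge figure comes from one count per child: "outpatient narcotic use will be recorded based on amount of medication remaining". The end of the window is set by this instruction to families: "Patients will be instructed to bring their medications with them to their first post-operative visit". No day or range is set for that visit. The nearest timing phrase, in Data Collection and Protection, is "re-admission in the immediate post-operative period (first two weeks post-operatively", which qualifies re-admission and not the visit.

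The opioid supply at discharge, in Post-Operative Protocol, is "oxycodone (0.1mg/kg PO or per g-tube every 6 hours as needed for severe pain, 20 doses". Nothing is said about refills.

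The primary outcome has a fixed window: "The primary outcome measure will be total narcotic consumption in the first 48 hours after surgery". Inpatient and outpatient use are both recorded in morphine equivalents, but no outcome adds them together.

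The Statistical Analysis Plan compares quantitative outcomes by t-test or Mann-Whitney test. It says that t-tests of narcotic use will cover comparable periods, but defines none for this outcome and gives no adjustment for window length.

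**The concern.** The start of the window is an event after randomization that the treatment may change. Take two children with the same need on each post-operative day. The one who goes home a day earlier has that day's doses counted as outpatient use. The other child's doses for that day are given in hospital after hour 48, so they fall in neither the primary outcome nor the post-discharge total.

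If the injection shortened stay, the active arm would show higher home use without any greater need. A report could then present a benefit (going home sooner) as a cost (more opioid), or miss a modest fall in need that the shift cancels out. The undated visit adds to this: totals over windows of unknown and unequal length are hard to compare between children or with other studies.

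**Working it through.** The plan gives no sample size, length of stay, visit day or rate of use, so there is no figure of its own to reproduce. The mechanism can be checked, and its size bounded under assumptions.

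**From the documents.** Supply of 20 doses; at most one dose every 6 hours, so 4 per day; two-sided test at 0.05; primary window of 48 hours. The supply lasts at least 20 / 4 = 5 days, so it can run out before the visit.

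**Assumed.** Need is identical in both arms: 2.5 doses/day on day 2, halving every 3 days. Mean stay is 4 days (SD 1, minimum 2) and the visit falls on day 10 to 21.

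**Hand calculation for an average child.** With discharge on day L and visit on day V:

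home doses = (2.5 × 3 / ln 2) × [2^(−(L−2)/3) − 2^(−(V−2)/3)], where 2.5 × 3 / ln 2 = 10.82.

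For V = 14 the last term is 2^(−4) = 0.0625.

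- L = 4: 10.82 × (0.6300 − 0.0625) = 6.14
- L = 3.5: 10.82 × (0.7071 − 0.0625) = 6.97, or +0.83
- L = 3: 10.82 × (0.7937 − 0.0625) = 7.91, or +1.77

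Counted from hour 48 to day 14, the total is 10.82 × (1 − 0.0625) = 10.14 whatever L is.

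**Simulation.** Adding variation between children, the day-2 minimum stay, the 4-per-day limit and the 20-dose ceiling makes the shifts smaller. Mean control use is about 6.1 doses.

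| Stay shorter by | Added home doses | Rejection, 20 to 50 per arm |
|---|---|---|
| 0.5 day | about 0.5 to 0.7 | 5 to 10% |
| 1 day | about 1.3 | 12 to 22% |
| Either, counted from hour 48 to visit | – | 4 to 6% |

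These rates depend on the assumed spread between children; another run of the same model gave up to 27.0% for one day at 50 per arm. The simulation counts doses. The plan counts morphine equivalents, so differences in weight would add spread and lower the rates.

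**Does the direction depend on the model?** A second model used starting rates of 1, 2 or 4 doses/day, decay rates of 0, 0.1 or 0.3 per day, stays of 3 against 5 days, and a visit 14 days from surgery or from discharge. With need identical, the shorter-stay arm had the higher ceiling-limited count in 15 of 18 scenarios:

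- visit timed from surgery: +0.7 to +4.2 doses
- visit timed from discharge, declining use: +1.1 to +4.1 doses
- visit timed from discharge, flat use (the 3 exceptions): about 0

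**The ceiling.** In the heaviest flat-use scenario it cut the difference from +5.8 to +0.7 doses. It shrinks the shift and does not create it.

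**Would a per-day rate solve it?** Using the first formula from hour 48, visits on days 10, 14 and 21 give totals of 9.12, 10.14 and 10.69 doses. Divided by 8, 12 and 19 days these are 1.14, 0.845 and 0.563 per day. The total rises by (10.69 − 9.12) / 9.12 = 17%; the rate falls by (1.14 − 0.563) / 1.14 = 51%. Because use declines, dividing by days makes the result more sensitive to visit date.

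**The case against.** The strongest reply concerns what is being estimated. The outcome named is home use. Because children are randomized, the comparison between arms validly estimates the injection's total effect on home use, including any part that acts through earlier discharge. A one-day shorter stay really does move doses into the home, so 12 to 22% rejection is detection of a true difference in the outcome as defined, not an inflated type I error. This stands. A reader might infer that the comparison is invalid or biased; the documents do not support that. What fails is the step from more home use to more need.

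Three further points stand in part.

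- **No difference in stay is documented.** Length of stay is only listed as an outcome, and every child has an epidural until the morning of day two. The problem is conditional. Still, the plan lists stay for comparison, so it allows for a difference.
- **The visit date is not tied to arm.** On its own an undated visit adds noise, not a systematic shift. It is also tempting to blame the 20-dose supply, but that is a separate limit: it compresses differences and, with any unrecorded refill, hides further use.
- **The planned mixed model of narcotic use over time could cover inpatient doses after hour 48.** Its window is not defined, and it cannot use the home data day by day, because the supply count gives one undated total per child.

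**Conclusion.** The point holds as a matter of interpretation for one secondary outcome. As written, a shorter stay in one arm would appear as higher post-discharge opioid use with no difference in need: about 0.5 to 0.7 dose for half a day and about 1.3 doses for one day, on a control mean of about 6.1. The direction needs only a difference in stay and either a visit timed from surgery or use that declines over time. The size rests on assumed stay, rate of use, decline and spread, none of which the documents give. The primary outcome, with its fixed 48-hour window, is untouched. This is a cheap improvement, not a serious fault.

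**What to change.** 1. Add, as the between-arm comparison of later opioid need, total morphine equivalents from hour 48 (or from surgery) to the first visit: recorded inpatient doses plus doses used from the discharge supply. Starting at surgery avoids having to date home doses for any child discharged before hour 48.
2. State a visit window measured from surgery, record the discharge and visit dates, and check sensitivity to visit day. Do not divide by days.
3. Keep post-discharge use as a separate home-use outcome, and state that it is to be read alongside length of stay and not as a measure of need.
4. Report by arm the proportion who used all 20 doses and any refill noted at the visit. The combined total still carries the ceiling in its home part.

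The cost is wording in Outcome Measures and the Statistical Analysis Plan, two dates per child and one question at the visit. The inpatient doses and the supply count are already to be collected. The documents do not say that refill prescriptions are captured, so refills should be asked about at the visit. The downside is that the combined total does not isolate home use, which is why the existing outcome is kept.

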Official Title: Efficacy of a Peri-Operative Surgical-Site, Multimodal Drug Injection in Pediatric Patients with Cerebral Palsy Undergoing Hip Surgery: A Randomized Controlled Trial.

NCT: NCT04074265

Date of Document: 1/4/2024

Study Title:

Efficacy of a Peri-Operative Surgical-Site, Multimodal Drug Injection in Pediatric Patients with Cerebral Palsy Undergoing Hip Surgery: A Randomized Controlled Trial.

Study Design:

This study is a prospective, randomized controlled trial with 2 parallel arms. Patients will be randomly assigned to the 2 treatment groups: surgical-site injection with ropivacaine, ketorolac, and epinephrine, or surgical-site injection with normal saline. Randomization will be performed via random number generator and will be carried out by a research associate who will not participate in study recruitment or outcomes assessment. Allocations will be concealed on a password-protected database accessible only to the research associate. Patients, surgeons, and nursing staff who perform post-operative assessments will be blinded to treatment allocation.

Participants:

Patients will be eligible to be included in this study if they are under the age of 18 years, have a known diagnosis of cerebral palsy, and are scheduled to undergo surgery of the proximal femur (specifically, unilateral or bilateral proximal femoral osteotomy for hip dysplasia). Patients will be recruited from both UCLA/Orthopaedic Institute for Children and Lurie Children's Hospital of Chicago. Patients and parents/guardians will be asked at their pre-operative clinic visit if they would like to participate in the study. They will be provided with the informed consent form at their pre-operative visit in order to allow them time to review the information prior to signing consent. Informed consent for the study will then be obtained in the pre-operative holding area prior to surgery. Patients will be excluded from the study if they have ongoing pre-operative opioid use, or a history of an allergic reaction to any of the components of the pain injection.

Surgical Procedure:

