Patients undergoing unilateral or bilateral hip proximal femoral osteotomies will be included in the study. All patients will be treated with standard-of-care techniques chosen by the treating surgeon. The addition of pelvic osteotomies and/or soft tissue procedures will be at the discretion of the treating surgeon and will not exclude the patient from the study. Written consent will be obtained for all patients prior to the surgical procedure. Parental consent will be obtained, in addition to patient assent for all patients of appropriate age and intellectual capability. All patients will have a general anesthetic with a lumbar epidural. No preemptive scheduled analgesic regimen will be employed. All medications administered during induction and maintenance of anesthesia will be managed by the anesthesiologist and titrated at their discretion.

The local anesthetic group will be injected with ropivacaine 2mg/mL (3mg/kg), epinephrine 1mg/mL (0.5mg), and ketorolac 30mg/mL (0.5mg/kg). If bilateral hips are involved, the total amount will be split evenly between the two sides. The control group will receive equivalent volumes of 0.9% sodium chloride solution (these volumes will be calculated based on the volumes of medication the patient would have received had they been assigned to the cocktail group). The injections will be performed while the patient is still under general anesthesia,

following wound closure, and medications will be injected evenly between the deep and superficial tissues in an extra-articular pattern (no injection of the synovium or capsule). All injections will be performed using a 20-gauge needle. The injection medications will be placed in a sterile cup. The surgical technician will fill syringes from the labeled cup, which will be handed to the surgeon for immediate administration.

Post-Operative Protocol:

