Outcome measures will be analyzed using a two-tailed t-test or a non-parametric Mann-Whitney test for quantitative variables; a Fischer exact test was used for categorical variables. Further, while a t-test will be utilized to demonstrate differences in narcotic consumption and average pain scores during *discrete, comparable, clinically-relevant measures of time*, mixed effects modeling will be utilized to further analyze narcotic consumption and pain scores *over time*. Statistical significance will be defined as p<0.05.

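### The primary 48-hour narcotic comparison has no site term; adding hospital to the t-test and to the rank test alike is an optional, cheap precision gain, not the correction of an error

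*Combined protocol and SAP*

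**What the plan says.** **Analysis.** The Statistical Analysis Plan states: "Outcome measures will be analyzed using a two-tailed t-test or a non-parametric Mann-Whitney test for quantitative variables". No covariate, stratum or site term is attached. A mixed effects model is also planned, but for narcotic use and pain scores over time. Its terms are not listed and site is not mentioned.

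**Outcome.** Under Outcome Measures: "The primary outcome measure will be total narcotic consumption in the first 48 hours after surgery". Narcotics given in the recovery unit and on the ward are both recorded.

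**Sites and allocation.** Under Participants: "Patients will be recruited from both UCLA/Orthopaedic Institute for Children" and a second hospital in Chicago. Under Study Design: "Randomization will be performed via random number generator", with no stratification by site described.

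**Discretion.**
- Recovery-unit drugs (Post-Operative Protocol): "will be prescribed by the attending anesthesiologist and will not be standardized".
- Rescue (same section): "Additional medication for pain may be administered if the protocol does not result in adequate pain relief, at the discretion of the treating physician".
- Epidural (same section): "The epidural will be titrated by the acute pain anesthesiology team for inadequate pain control".
- Extent of surgery (Surgical Procedure): "The addition of pelvic osteotomies and/or soft tissue procedures will be at the discretion of the treating surgeon".

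**Standardization.** The Post-Operative Protocol also sets a common weight-based regimen from the time a patient leaves the recovery unit. Oxycodone is reserved for pain scores of 7 to 10, as-needed drugs are offered every 4 hours, and all epidurals stop on the morning of post-operative day two.

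**The concern.** Hospital is known for every patient before randomization. Part of the primary outcome is set by clinicians' choices, and the two hospitals presumably have different clinicians. If mean opioid use differs between the hospitals, that difference stays in the error term of an unadjusted test, widens the confidence interval and lowers power. A site term removes the difference between hospital means. It does not remove variation between clinicians within a hospital.

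What is at stake is precision only. Randomization protects the comparison between arms, and no bias is claimed.

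**Working it through.** **1. Inputs.** From the documents: two arms, two hospitals, a two-sided test at 0.05, no stated stratification by site. Not in the documents, so assumed: number of patients N, equal arms, share q of patients at one hospital, and difference d between hospital means in within-hospital SDs. The plan gives no power or sample size figure to reproduce.

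**2. Variance formula.** With site independent of arm, the variance facing the unadjusted test, relative to the within-hospital variance, is V = 1 + q(1−q)d². For a test with 80% power at d = 0, power becomes Φ(2.802/√V − 1.960), where 2.802 = 1.960 + 0.842.

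| d | V, q = 0.5 | Power | V, q = 0.2 | Power |
|---|---|---|---|---|
| 0.25 | 1.016 | 79.4% | 1.010 | 79.6% |
| 0.5 | 1.063 | 77.6% | 1.040 | 78.4% |
| 1.0 | 1.250 | 70.7% | 1.160 | 73.9% |

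Example: q = 0.5, d = 1 gives V = 1 + 0.25 = 1.25, and Φ(2.802/1.118 − 1.960) = Φ(0.546) = 70.7%.

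**3. Simulated power (%), normal errors, q = 0.5, allocation not stratified by site.** There were 20,000 to 40,000 trials per cell. Each pair starts near 80% for its own unadjusted test, so compare within a pair and not across columns.

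| N | d | t-test → arm + site | Mann-Whitney → van Elteren |
|---|---|---|---|
| 40 | 0 | 79.9 → 78.8 (−1.1) | 79.6 → 77.8 (−1.8) |
| 40 | 0.5 | 77.3 → 78.8 (+1.5) | not run |
| 40 | 1.0 | 70.5 → 78.7 (+8.2) | not run |
| 60 | 0 | 80.1 → 79.4 (−0.7) | 79.8 → 78.2 (−1.6) |
| 60 | 0.25 | 79.4 → 79.2 (−0.2) | 78.8 → 78.2 (−0.6) |
| 60 | 0.5 | 77.5 → 79.4 (+1.9) | 77.1 → 78.3 (+1.2) |
| 60 | 1.0 | 70.5 → 79.3 (+8.8) | 69.6 → 78.3 (+8.7) |
| 100 | 0 | 79.9 → 79.5 (−0.4) | not run |
| 100 | 0.5 | 76.9 → 79.0 (+2.1) | not run |
| 100 | 1.0 | 70.4 → 79.6 (+9.2) | not run |

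Type I error of the t-test and of the linear model was 4.6% to 5.3% throughout. With N = 60 and a 20/80 split, the linear model changes power by −0.8 (79.6 → 78.8), +1.0 (78.6 → 79.6) and +5.3 (74.0 → 79.3) points at d = 0, 0.5 and 1.0.

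**4. Break-even for the linear model.** Chance imbalance in site between the arms inflates the adjusted variance by about 1/N. The site term therefore pays once q(1−q)d² exceeds 1/N, that is, d = 1/√(N q(1−q)). At q = 0.5 this is 0.32, 0.26 and 0.20 for N = 40, 60 and 100. For the rank pair at N = 60, break-even lies between d = 0.25 and d = 0.5.

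**5. Skewed outcomes.** Log-normal data, N = 60, q = 0.5, d = 0.5 on the log scale, assumed log-SD 0.75:
- t-test 65.7% → linear model with site 67.1% (+1.4)
- Mann-Whitney 74.4% → van Elteren 76.3% (+1.9)
- Mann-Whitney 74.4% → linear model with site 67.1% (−7.3)

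At log-SD 1.0 the last switch goes from 74.4% to 59.2% (−15.2). At log-SD 0.5 it is close to neutral (74.9% to 74.0%). Adding site helps within each family. Replacing the rank test by a linear model can cost several times what site returns.

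**The case against.** The strongest case against raising this is that nothing in the plan is wrong. The test is valid, and no site-stratified randomization is described that the analysis ought to mirror. The discretion in the protocol belongs to individual anesthesiologists, surgeons and physicians, which is not the same as a difference between hospital means. The common ward regimen covers most of the 48 hours and makes a large hospital difference less likely. The larger gains need an assumed difference of a full SD.

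All of this stands, and it sets the weight of the point. It does not remove the point: recovery-unit opioids count before the common regimen starts, rescue drugs and epidural titration sit on top of it, and the planned mixed model does not supply a site term.

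A reader might infer three stronger things, and the documents support none of them:
- **The unadjusted result would be biased or invalid.** Allocation is random, and simulated type I error stays near 5%.
- **The two hospitals do differ in opioid use.** No document says so. It is a plausible inference from clinician discretion and no more.
- **The linear model should become the sole primary analysis, with the rank test as support.** The plan allows either test. As-needed opioid totals in children of widely varying weight may well be skewed, and step 5 of the working shows the loss that could follow.

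**Conclusion.** The point holds as an optional improvement in precision. With 40 to 100 patients and equal hospital shares, the benefit is about 1 to 2 points of power at a hospital difference of 0.5 SD and about 8 to 9 points at 1 SD. At 0.25 SD and 60 patients, adding site is a slight net loss. If the hospitals do not differ, the cost is about 2 points at most: up to 1.1 for the linear model and 1.8 for the rank test at 40 patients. In a smaller trial of 30 patients the linear model loses 1.6 points (80.3% to 78.7%). Unequal enrolment shrinks the gain.

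All of these sizes rest on assumed N, q, d and outcome distribution, because the documents give none of them. What comes from the documents is that there are two hospitals, that part of the outcome is left to clinicians, and that no site term is planned.

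**What to change.** Before unblinding, add one sentence to the Statistical Analysis Plan for the primary 48-hour outcome. Wherever the t-test would be used, fit a linear model with arm and site. Wherever Mann-Whitney would be used, apply the site-stratified rank test (van Elteren). Leave the plan's choice between parametric and rank tests as it is, and do not reduce the rank test to a supporting analysis. If the data are already unblinded, keep the planned test and report the site-adjusted result as a labelled sensitivity analysis.

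The cost is one sentence and one model term (one degree of freedom). It needs no extra patients, procedures or data, since each patient's hospital is already known.
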